6.8.8. Rescue Medicine

There is no rescue therapy to reverse the AEs observed with PF-07260437; standard medical supportive care must be provided to manage the AEs.

7. DISCONTINUATION OF STUDY INTERVENTION AND PARTICIPANT DISCONTINUATION/WITHDRAWAL

7.1. Discontinuation of Study Intervention

It may be necessary for a participant to permanently discontinue study intervention. Reasons for permanent discontinuation of study intervention may include the following:

- Objective disease progression;
- Global deterioration of health status requiring discontinuation;
- Unacceptable toxicity;
- Pregnancy;
- Significant protocol violation;
- Lost to follow-up;
- Participant refused further treatment;
- Study terminated by sponsor;
- Death;

Note that discontinuation of study intervention does not represent withdrawal from the study. If study intervention is permanently discontinued, the participant will remain in the study to be evaluated for safety follow-up and survival follow-up (Part 2). See the [SOA](#) for data to be

collected at the time of discontinuation of study intervention and follow-up for any further evaluations that need to be completed.

In the event of discontinuation of study intervention, it must be documented on the appropriate CRF/in the medical records whether the participant is discontinuing further receipt of study intervention or also from study procedures, posttreatment study follow-up, and/or future collection of additional information.

Safety Follow-Up:

At least 28 calendar days, and no more than 35 calendar days after discontinuation of study intervention, participants will return to undergo review of concomitant treatments, vital signs, and assessment for resolution of any treatment related AEs. Participants continuing to experience AEs at this point following discontinuation of treatment will continue to be followed at least every 4 weeks until resolution or determination, in the clinical judgment of the investigator, that no further improvement is expected. If the unresolved AE is considered by the investigator as possibly related to or associated with ADA formation, the participant will be asked to return for drug concentration and ADA blood sampling at up to 3-month intervals, until the last follow-up of the AE.

For part 2 of the study, survival status will be collected by telephone every 3 months until death, or up to 24 months after first dose of the last participant.

7.1.1. ECG Changes

A participant who meets either bulleted criterion based on the average of triplicate ECG readings will be withdrawn from the study intervention.

- QTcF >500 msec.
- Change from baseline: QTcF >60 msec and QTcF > 450 msec.

If a clinically significant finding is identified (including, but not limited to, changes from baseline in QTcF after enrollment), the investigator or qualified designee will determine if the participant can continue in the study and if any change in participant management is needed. This review of the ECG printed at the time of collection must be documented. Any new clinically relevant finding should be reported as an AE.

7.2. Participant Discontinuation/Withdrawal From the Study

A participant may withdraw from the study at any time at their own request. Reasons for discontinuation from the study may include:

- Refused further study procedures;
- Lost to follow-up;
- Death;
- Study terminated by sponsor.

If a participant withdraws from the study, he/she may request destruction of any remaining samples taken and not tested, and the investigator must document any such requests in the site study records and notify the sponsor accordingly.

If the participant withdraws from the study and also withdraws consent (see Section 7.2.1) for disclosure of future information, no further evaluations should be performed and no additional data should be collected. The sponsor may retain and continue to use any data collected before such withdrawal of consent.

7.2.1. Withdrawal of Consent

Participants who request to discontinue receipt of study intervention will remain in the study and must continue to be followed for protocol-specified follow-up procedures. The only exception to this is when a participant specifically withdraws consent for any further contact with him or her or persons previously authorized by the participant to provide this information. Participants should notify the investigator in writing of the decision to withdraw consent from future follow-up, whenever possible. The withdrawal of consent should be explained in detail in the medical records by the investigator, as to whether the withdrawal is only from further receipt of study intervention or also from study procedures and/or posttreatment study follow-up, and entered on the appropriate CRF page. In the event that vital status (whether the participant is alive or dead) is being measured, publicly available information should be used to determine vital status only as appropriately directed in accordance with local law.

7.3. Lost to Follow-Up

A participant will be considered lost to follow-up if he or she repeatedly fails to return for scheduled visits and is unable to be contacted by the study site.

The following actions must be taken if a participant fails to return to the clinic for a required study visit:

- The site must attempt to contact the participant and reschedule the missed visit as soon as possible. Counsel the participant on the importance of maintaining the assigned visit schedule and ascertain whether the participant wishes to and/or should continue in the study.
- Before a participant is deemed lost to follow-up, the investigator or designee must make every effort to regain contact with the participant (where possible, 3 telephone calls and, if necessary, a certified letter to the participant's last known mailing address or local equivalent methods). These contact attempts should be documented in the participant's medical record.
- Should the participant continue to be unreachable, he/she will be considered to have withdrawn from the study.

8. STUDY ASSESSMENTS AND PROCEDURES

The investigator (or an appropriate delegate at the investigator site) must obtain a signed and dated ICD before performing any study-specific procedures.

Study procedures and their timing are summarized in the [SOA](#). Protocol waivers or exemptions are not allowed.

Safety issues should be discussed with the sponsor immediately upon occurrence or awareness to determine whether the participant should continue or discontinue study intervention.

Adherence to the study design requirements, including those specified in the [SOA](#), is essential and required for study conduct.

All screening evaluations must be completed and reviewed to confirm that potential participants meet all eligibility criteria. The investigator will maintain a screening log to record details of all participants screened and to confirm eligibility or record reasons for screening failure, as applicable.

Procedures conducted as part of the participant's routine clinical management (eg, blood count) and obtained before signing of the ICD may be utilized for screening or baseline purposes provided the procedures met the protocol-specified criteria and were performed within the time frame defined in the [SOA](#).

Every effort should be made to ensure that protocol-required tests and procedures are completed as described. However, it is anticipated that from time to time there may be circumstances outside the control of the investigator that may make it unfeasible to perform the test. In these cases, the investigator must take all steps necessary to ensure the safety and well-being of the participant. When a protocol-required test cannot be performed, the investigator will document the reason for the missed test and any corrective and preventive actions that he or she has taken to ensure that required processes are adhered to as soon as possible. The study team must be informed of these incidents in a timely manner.

For samples being collected and shipped, detailed collection, processing, storage, and shipment instructions and contact information will be provided to the investigator site prior to initiation of the study.

8.1. Efficacy Assessments

8.1.1. Tumor Response Assessments

Tumor assessments will include all known or suspected disease sites. Imaging will include contrast enhanced head, chest, abdomen, and pelvis computed tomography or MRI scans; brain computed tomography or MRI scan for participants with known or suspected brain metastases; bone scan and/or PET scan for all participants to monitor potential bone metastases. For participants with known computed tomography contrast allergy, a non-

contrast computed tomography of the chest with contrast enhanced abdominal and pelvic MRI can be used. The same imaging technique used to characterize each identified and reported lesion at baseline will be employed in the following tumor assessments.

Antitumor activity will be assessed through radiological tumor assessments conducted at baseline, during treatment every 8 weeks from C1D1 (± 7 days) for the first 6 months, every 12 weeks (± 7 days) for the next 18 months, and every 4 months thereafter as specified in the [SOA](#), whenever disease progression is suspected (eg, symptomatic deterioration), and at the time of withdrawal from treatment (if not done in the previous 4 weeks). Assessment of response will be made using RECIST version 1.1 (see [Appendix 12](#)) and irRECIST (See [Appendix 13](#)). Confirmation of response (CR/PR) with a second consecutive scan at least 4 weeks later is preferred.

All participants' files and radiologic images must be available for source verification and for potential peer review.

Antitumor activity will be assessed at baseline, during treatment as specified in the [SOA](#), whenever disease progression is suspected (eg, symptomatic deterioration), and at the time of withdrawal from treatment (if not done in the previous 4 weeks).

If imaging is used in disease assessment, the same imaging technique used to characterize each identified and reported lesion at baseline will be employed in post-baseline disease assessments.

8.2. Safety Assessments

Planned time points for all safety assessments are provided in [SOA](#). Unscheduled clinical laboratory measurements may be obtained at any time during the study to assess any perceived safety issues.

Safety assessments will include collection of AEs, SAEs, vital signs and physical examination, ECG (12-lead), laboratory assessments, including pregnancy tests and verification of concomitant treatments.

8.2.1. Physical Examinations

Participants will have a physical examination to include weight, vital signs, assessment of ECOG performance status and height; height will be measured at screening only. Refer to [Appendix 16](#) for ECOG performance status grading.

A complete physical examination will include more comprehensive assessments of the cardiovascular, respiratory, GI, genitourinary (if needed, musculoskeletal and neurological systems in addition to the assessments for the brief physical exam listed below.

A brief physical examination will include, at a minimum, assessments of skin, lungs, cardiovascular system, and abdomen (liver and spleen).

Investigators should pay special attention to clinical signs related to previous serious illnesses.

Physical examinations may be conducted by a physician, trained physician's assistant, or nurse practitioner as acceptable according to local regulation.

Height and weight will also be measured and recorded as per the [SOA](#). For measuring weight, a scale with appropriate range and resolution is used and must be placed on a stable, flat surface. Participants must remove shoes, bulky layers of clothing, and jackets so that only light clothing remains. They must also remove the contents of their pockets and remain still during measurement of weight.

Physical examination findings collected during the study will be considered source data and will not be required to be reported, unless otherwise noted. Any untoward physical examination findings that are identified during the active collection period and meet the definition of an AE or SAE ([Appendix 3](#)) must be reported according to the processes in [Sections 8.3.1 to 8.3.3](#).

When should it be done:

Physical examination should be completed prior to dosing.

8.2.2. Vital Signs

Oral temperature, pulse rate, respiratory rate, and BP will be assessed. BP and pulse rate measurements will be assessed in a sitting or semi-recumbent position (the same position should be maintained throughout the study) with a completely automated device. Manual techniques will be used only if an automated device is not available.

BP and pulse rate measurements should be preceded by at least 5 minutes of rest for the participant in a quiet setting without distractions (eg, television, cell phones).

Vital signs (to be taken before blood collection for laboratory tests) will consist of 1 pulse rate and 2 BP measurements (2 consecutive blood pressure readings will be recorded at intervals of at least 1 minute). The average of the 2 BP readings will be recorded on the CRF.

When should it be done:

Vital sign assessments should be completed prior to dosing.

8.2.3. Electrocardiograms

A single 12-lead ECG will be utilized as screening. A triplicate 12-lead ECGs will be utilized for Cycles 1 to 3 to determine mean QTcF interval. For the days of dose administration, perform ECG up to 60 minutes prior to dosing (SC or IV), and at the end of infusion (IV only).

From Cycle 4 onwards: Triplicate 12-lead ECG up to 60 minutes prior to dosing on Day 1 of every 3 cycles (C4D1, C7D1, etc.).

Standard 12-lead ECGs utilizing limb leads (with a 10 second rhythm strip) should be collected at times specified in the [SOA](#) section of this protocol using an ECG machine that automatically calculates the heart rate and measures PR, QT, and QTc intervals and QRS complex. Alternative lead placement methodology using torso leads (eg, Mason-Likar) should not be used given the potential risk of discrepancies with ECGs acquired using standard limb lead placement. All scheduled ECGs should be performed after the participant has rested quietly for at least 5 minutes in a supine position.

To ensure safety of the participants, a qualified individual at the investigator site will make comparisons to baseline measurements. Additional ECG monitoring will occur if a) the mean value from the triplicate measurements for any postdose QTcF interval is increased by ≥ 60 msec from the baseline and is > 450 msec; or b) an absolute QTcF value is ≥ 500 msec for any scheduled ECG. If either of these conditions occurs, then a single ECG measurement must be repeated at least hourly until QTcF values from 2 successive ECGs fall below the threshold value that triggered the repeat measurement. In addition, if verified QTcF values continue to exceed the criteria above, immediate correction for reversible causes including electrolyte abnormalities, hypoxia, and concomitant medications for drugs with the potential to prolong the QTcF interval should be performed.

If the QTcF interval reverts to less than the threshold criteria listed above, and in the judgment of the investigator(s) and sponsor, it is determined that the cause(s) of QTcF prolongation is something other than study intervention, treatment may be continued with regular ECG monitoring. If in that timeframe the QTcF intervals rise above the threshold values, the study intervention will be held until the QTcF interval decreases to below the threshold values. Participants will then restart the study intervention at the next lowest dose level. If the QTcF interval has still not decreased to < 480 msec after 2 weeks, or if at any time a participant has a QTcF interval > 515 msec or becomes symptomatic, the participant will be removed from the study. Additional triplicate ECGs may be performed as clinically indicated.

In some cases, it may be appropriate to repeat abnormal ECGs to rule out improper lead placement as contributing to the ECG abnormality. It is important that leads be placed in the same positions each time in order to achieve precise ECG recordings. If a machine-read QTc value is prolonged, as defined above, repeat measurements may not be necessary if a qualified medical provider's interpretation determines that the QTcF values are in the acceptable range.

ECG values of potential clinical concern are listed in [Appendix 7](#).

When should it be done:

- ECG assessments should precede blood collection for clinical laboratory tests if possible.

- **At screening:** single 12-lead ECG.
- **Cycles 1 to 3:** triplicate 12-lead ECGs to determine mean QTcF interval. For the days of dose administration, perform ECG up to 60 minutes prior to dosing (SC or IV), and at the end of infusion (IV only).
- **From Cycle 4 onwards:** Triplicate 12-lead ECG up to 60 minutes prior to dosing on Day 1 of every 3rd cycle.
- If a participant experiences a cardiac or neurologic AE (specifically syncope, dizziness, seizures, or stroke), an ECG (triplicate) should be obtained at or close to the time of the event.
- **End of Treatment and 4-week follow-up:** triplicate 12-lead ECG.

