9.3.5.1. Electrocardiogram Analyses

Changes from baseline for the ECG parameters QT interval, heart rate, QTcF, PR interval, and QRS complex will be summarized by treatment and time.

The number (%) of participants with maximum postdose QTcF values and maximum increases from baseline in the following categories will be tabulated by treatment:

Safety QTcF Assessment

Degree of Prolongation	Mild (ms)	Moderate (ms)	Severe (ms)
Absolute value	>450-480	>480-500	>500
Increase from baseline		30-60	>60

If more than 1 ECG is collected at a nominal time after dose administration (for example, triplicate ECGs), the mean of the replicate measurements will be used to represent a single observation at that time point. If any of the 3 individual ECG tracings has a QTcF value >500 ms, but the mean of the triplicates is not >500 ms, the data from the participant's individual tracing will be described in a safety section of the CSR in order to place the >500 ms value in appropriate clinical context. However, values from individual tracings within triplicate measurements that are >500 ms will not be included in the categorical analysis unless the average from the triplicate measurements is also >500 ms. Changes from baseline will be defined as the change between the postdose QTcF value and the average of the time-matched baseline triplicate values on Day -1, or the average of the predose triplicate values on Day 1.

In addition, an attempt will be made to explore and characterize the relationship between plasma concentration and QT interval length using a PK/pharmacodynamics modeling approach. If a PK/pharmacodynamics relationship is found, the impact of participant factors (covariates) on the relationship will be examined.

The analysis of ECG results will be based on participants in the safety analysis set with baseline (pre-dose on Cycle 1 Day 1) and on-treatment ECG data.

ECG measurements (an average of the triplicate measurements) will be used for the statistical analysis and all data presentations. Any data obtained from ECGs repeated for safety reasons after the nominal time points will not be averaged along with the preceding triplicates. Interval measurements from repeated ECGs will be included in the outlier analysis (categorical analysis) as individual values obtained at unscheduled time points.

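### Protocol 7.1.1 withdraws study drug for QTcF prolongation after which 8.2.3 permits continuation or directs a restart, with no stated precedence; 8.2.3 also takes the worst cases off study

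*Protocol*

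**What the plan says.** Four parts of the protocol bear on what happens after QTcF prolongation.

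- **7.1.1 ECG Changes.** The criteria are a QTcF above 500 msec, or a rise of more than 60 msec with QTcF above 450 msec. The consequence is: "A participant who meets either bulleted criterion based on the average of triplicate ECG readings will be withdrawn from the study intervention". A following paragraph lets the investigator decide, for clinically significant findings, whether the participant can stay in the study and whether management should change.
- **8.2.3 Electrocardiograms.** The triggers are (a) a triplicate-mean rise of at least 60 msec with QTcF above 450 msec, or (b) an absolute QTcF of at least 500 msec on any scheduled ECG. Single ECGs are then repeated at least hourly "until QTcF values from 2 successive ECGs fall below the threshold value that triggered the repeat measurement". Once QTcF has reverted, dosing turns on a joint judgment by sponsor and investigator about cause; where "it is determined that the cause(s) of QTcF prolongation is something other than study intervention, treatment may be continued with regular ECG monitoring". When it rises again, "the study intervention will be held until the QTcF interval decreases to below the threshold values", after which "Participants will then restart the study intervention at the next lowest dose level". If QTcF is not below 480 msec after 2 weeks, or if the participant at any time exceeds 515 msec "or becomes symptomatic, the participant will be removed from the study".
- **7.1 Discontinuation of Study Intervention.** Stopping drug is not leaving the study: "the participant will remain in the study to be evaluated for safety follow-up and survival follow-up (Part 2").
- **4.3.6.2 and 6.5.3.** Grade 3 QTcF prolongation that persists after reversible causes are corrected is a DLT. A participant with a DLT may resume at the next lower dose after adequate recovery if judged to be benefiting.

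Neither 7.1.1 nor 8.2.3 refers to the other, and no other text ranks them.

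**The concern.** Sections 7.1.1 and 8.2.3 address almost the same QTcF values and give different instructions on further dosing. A site working from 8.2.3 alone could re-dose a participant whom 7.1.1 takes off drug, and on re-elevation would be told to do so. This is a first-in-human study without a DMC, so the rule for stopping or re-dosing after a cardiac signal should have one reading.

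The second problem is where the worst cases go. Leaving the study is a different event from stopping drug, and 8.2.3 uses the former for the most severe prolongation. The list of reasons for leaving the study in 7.2 is not exhaustive, but it contains no ECG reason.

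The effect on the analysis is minor. The rule applied feeds the discontinuation table (SAP 6.5.2) and the interruption and reduction summaries (SAP 6.5.3). It can also decide DLT evaluability for a Part 1 participant without priming. One who has no DLT and is withdrawn after the C1D1 dose alone for a non-drug cause is not evaluable (9.1.1.1), whereas one who continues to C1D15 can be.

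**Working it through.** No sample size or error rate is involved, so the check applies both rules to the same values (all in msec).

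**Inputs.** Withdrawal under 7.1.1: mean > 500, or rise > 60 and mean > 450. Triggers in 8.2.3: rise ≥ 60 and > 450, or ≥ 500. Off-study criteria in 8.2.3: > 515, symptoms, or not < 480 after 2 weeks. Baseline limit for eligibility (5.2): 470.

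**Overlap.** Take every integer pair of baseline 380 to 470 (the lower bound is illustrative) and post-dose mean from baseline to 540. Of these, 5,415 meet 7.1.1, and all of them also meet an 8.2.3 trigger. They divide into 3,140 at or below 515, where the continue or restart path can be open, and 2,275 above it (3,140 + 2,275 = 5,415). A further 80 pairs trigger 8.2.3 only. These are logical cells, not patient frequencies.

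**Case A: first episode.** Baseline 410, mean 475 (475 − 410 = 65), later 440, asymptomatic, non-drug cause agreed. Section 7.1.1 withdraws; 8.2.3 says treatment *may* continue. Withdrawing complies with both sections; continuing complies with 8.2.3 only.

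**Case B: re-elevation with no earlier breach of 7.1.1.** Baseline 450.
1. Tracings 503, 498, 494: mean 1495/3 = 498.3, rise 48.3. Section 7.1.1 is not met. Trigger (b) is met if read per tracing. QTcF falls to 470, a non-drug cause is agreed, and treatment continues.
2. Tracings 506, 504, 502: mean 1512/3 = 504, rise 54, asymptomatic. Section 7.1.1 is met and withdraws. Under 8.2.3 drug is held, QTcF is 472 on day 10, and the participant *will* restart one level down. Both cannot be done.

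The per-tracing reading is plausible. Trigger (a) names the triplicate mean and (b) does not, and Section 9.3.5.1 foresees the split: "If any of the 3 individual ECG tracings has a QTcF value >500 ms, but the mean of the triplicates is not >500 ms". It is also not essential. A first mean of exactly 500 from baseline 445 (rise 55), or a rise of exactly 60 from 410 to 470, triggers 8.2.3 and not 7.1.1. A second episode above 500 then gives the same clash.

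**Attribution.** In 8.2.3 the non-drug judgment is attached to continuing after the first episode. The hold and restart sentences that follow carry no attribution condition, so they cover a re-elevation that is attributed to study drug.

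**Post-DLT route.** Sections 4.3.6.2 and 6.5.3 together allow resumption after a QTcF DLT. The documents do not give the CTCAE grade cut-points for QTcF, so the overlap with 7.1.1 is not counted here.

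**Case D: worst cases.** Take episode 2 of case B, but with a peak of 520, or symptoms, or a value of 485 at 2 weeks. Drug stops under both sections. Under 7.1.1 with 7.1 the participant stays in follow-up; under 8.2.3 the participant is off study.

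**Size.** The documents give no QTcF event rate. Assume that 1% to 5% of about 100 participants meet 7.1.1, and that 25% to 50% of those satisfy the remaining 8.2.3 conditions:
- low: 0.01 × 100 × 0.25 = 0.25
- high: 0.05 × 100 × 0.50 = 2.5

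A directed restart also needs a second episode, so fewer would reach it.

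**The case against.** The best defence is that the two sections do different jobs. Section 7.1.1 is the stopping rule, on triplicate means. Section 8.2.3 is a more sensitive monitoring rule, with ≥ thresholds, any scheduled ECG and hourly repeats, and its continue and hold provisions have their own territory where 7.1.1 is not met. Its first-episode wording is only permissive. The second paragraph of 7.1.1 leaves room for judgment, and Section 8 requires immediate sponsor discussion of whether dosing should continue.

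Much of this stands. It is the sensible joint reading, and the fix simply writes it down. But the protocol does not state it. The 7.1.1 paragraph concerns remaining in the study, does not mention 8.2.3 and does not restore dosing. Section 8 requires a conversation without naming the governing rule, and it also bars waivers. The restart sentence is an instruction, not a permission.

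On follow-up, the defence narrows the harm. Section 8.3.1 keeps AE collection for at least 28 days after the last dose, and leaving the study shortens this only if consent is also withdrawn. Section 8.3.3 requires follow-up until the event resolves or stabilizes. What remains exposed is the scheduled follow-up visits and the Part 2 survival contacts. The visits include the 4-week triplicate ECG that 8.2.3 itself schedules.

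**Conclusion.** The inconsistency is real and should be fixed, but it is narrow. The direct clash is confined to a re-elevation whose triplicate mean meets 7.1.1, is at or below 515 msec, is asymptomatic and resolves. On the assumed rates above, at most a few participants would meet differing dosing instructions. No hypothesis test or error rate is affected, and a participant who is not DLT-evaluable may be replaced (4.3.6).

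Four stronger readings are tempting and not supported:
- **That sites are forced to choose in a first episode.** They are not; withdrawing satisfies both sections.
- **That 8.2.3 allows dosing to continue after any drug-attributed prolongation.** For a first episode it gives no such path. Only the re-elevation wording is silent on cause.
- **That the off-study wording ends all safety follow-up.** Sections 8.3.1 and 8.3.3 keep AE collection and follow-up.
- **That ≥ in 8.2.3 against > in 7.1.1 is an error.** A monitoring trigger slightly more sensitive than the stopping rule is reasonable, and ≥ 60 msec also appears in protocol Appendix 7 and SAP Appendix 2.

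**What to change.** 1. Add to 8.2.3, with cross-references in 7.1.1 and 6.5.3, wording such as: *When the triplicate-mean criteria of Section 7.1.1 are met, Section 7.1.1 governs and study intervention is withdrawn. The continuation, hold and restart provisions of this section, and resumption after a DLT for QTcF prolongation under Section 6.5.3, apply only when those criteria are not met.*
2. In 8.2.3, change *removed from the study* to *withdrawn from study intervention*, so that scheduled safety follow-up and Part 2 survival follow-up continue as 7.1 states.

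The ≥ monitoring triggers in 8.2.3 can stay. The cost is amendment wording in three sections, with no new assessments, participants or analyses.
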